#### 5.12.4 Return or Destruction of Study Drug

Regular study drug reconciliation will be performed at the end of the study. Drug that was assigned, drug consumed, and drug remaining will be logged in the drug accountability form and will be signed and dated.

At the completion of the study, there will be a final reconciliation of drug purchased, drug consumed, and drug remaining. This reconciliation will be logged on the drug reconciliation form, signed and dated. Any discrepancies noted will be investigated, resolved, and documented prior to destruction of unused study drug. Drug destroyed on site will be documented in the study files.

## **6.0 STUDY PROCEDURES**

A schedule of events can be found in Appendix A.

### **6.1 Study Visit Schedule**

Screening: Trial Coordinator will screen the office charts for possible inclusion in the trial. Labs for the screening part will be available from pre-admission testing that is standard of care.

Visit 1: Subjects that meet the inclusion criteria after reviewing the initial biopsy, laboratory data and clinical chart will be approached the day of their follow up after initial biopsy. The study coordinator will meet with the prospective candidates and go over the protocol, answer questions and obtain informed consent. If the subject is agreeable to the study, a physical exam will be performed, blood and saliva will be collected, and participant will be randomized.

Metformin/placebo Instructions on how to take study drug will be given and times for follow up phone calls for tolerability and safety will be arranged with participants. Participants will be instructed to call with any side effects or adverse events that occur in the interim of the follow up phone calls. The exact date to start the metformin will be determined this visit based on the planned start of radiation. Subject will be instructed to start taking the metformin/placebo at any point from 1 to 7 days from the start of radiation.

Quality of life measures including the EORTC QLQ – H&N35, mucositis score, Multidimensional fatigue inventory and the Xerostomia Questionnaire (XQ) will be administered on an iPad through the website ([https://az1.qualtrics.com/jfe6/preview/SV\\_87y9lyJ0sFo8oJv](https://az1.qualtrics.com/jfe6/preview/SV_87y9lyJ0sFo8oJv)). Patients will be identified only by an ID number.

Visit 2: Subjects will come in during the 3rd week of their radiation for blood draw, saliva collection, physical exam, quality of life questionnaires and tolerability assessment. An inventory of medication will also be taken to assess compliance. Location of radiation is not dictated by this protocol.

Visit 3: Two weeks after completion of radiation. Subjects will be approached for bottle and pill reconciliation as well as follow up of side effects and adverse events. Blood and saliva will be collected, and MD Anderson Dysphagia Inventory, Multidimensional fatigue inventory (MFI-20) and the Xerostomia Questionnaire (XQ) will be administered will be administered on an iPad through the website ([https://az1.qualtrics.com/jfe6/preview/SV\\_87y9lyJ0sFo8oJv](https://az1.qualtrics.com/jfe6/preview/SV_87y9lyJ0sFo8oJv)). Patients will be identified only by an ID number.

Follow-up: Every 3 months during the 1st year post treatment subjects will have their regularly schedule appointments at which we will draw blood and saliva and administer quality of life surveys. The participant's medical records will be reviewed every 3 months for 12 months.

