## Study Summary

|  |   |
|--|---|
| Title                                    | Pilot study of metformin in head and neck cancer and its effect on proinflammatory cytokines and exosomes implicated in acute and chronic toxicity   |
| Short Title                              | Metformin in radiation treatment of head and neck cancer   |
| Protocol Number                          | IRB# 16D.639/JT#9410   |
| Phase                                    | Pilot   |
| Methodology/Study Design                 | Pilot Feasibility trial   |
| Study Duration                           | 24 months   |
| Study Center(s)                          | Single Center- Jefferson  |
| Objectives                               | To assess the effect of metformin on radioprotection in normal tissue for subjects undergoing head and neck radiation. We will evaluate metformin's ability to decrease proinflammatory cytokines and decrease mucositis, xerostomia, fatigue and dysphagia.  |
| Number of Subjects                       | 50  |
| Diagnosis and Main Inclusion Criteria    | Subjects with a biopsy proven diagnosis of head and neck cancer, and who have a scheduled appointment for either postoperative adjuvant radiation or definitive radiation.  |
| Study Therapy, Dose, Route, Regimen      | Metformin is the therapeutic agent in the protocol. The initial starting dose will be 500mg orally daily for 3 (+2 days) days which then will be increased to 500 mg twice daily and, if tolerated, further increased to 1000mg twice daily after day 6 (+2 days). Subjects will maintain 1000 mg twice a day dosing until two weeks post radiation. Subjects will be randomized to 1:1 to take metformin or placebo.   |
| Duration of administration and follow-up | The initial starting dose will be 500mg orally daily for 3 (+2 days) days which then will be increased to 500 mg twice daily and, if tolerated, further increased to 1000mg twice daily after day 6 (+2 days). Subjects will maintain 1000 mg twice a day dosing until two weeks post radiation. The participant's medical records will be reviewed every 3 months for 12 months. 2 vials of Blood and 5cc of saliva samples will be obtained before, during and immediately after treatment and every three months thereafter for one year |
| Reference therapy                        | None   |

|                                |   |
|--------------------------------|---|

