**Schema of the trial design, procedures, and stages:**

Patients with a head and neck region biopsy and diagnosis of HNSCC cancer who are planned to undergo definitive treatment by definitive radiation or up front surgery followed by adjuvant radiation. After informed consent is signed, patients will be administered metformin with dose escalation as tolerated\* until time of radiation.

\*Metformin (500 mg/day for 3 (+2 days) days followed by 500 mg twice daily for 3 days followed by 1000mg twice daily from day 6 (+2 days). Subjects will maintain 1000 mg twice a day dosing until two weeks post radiation. )

\*\* Placebo (1 tab taken BID) No ramp up phase

Participant's Follow-up. The participant's medical records will be reviewed every 3 months for 12 months to assess: Mucositis, xerostomia, fatigue and dysphagia

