## 4.0 SUBJECT SELECTION AND WITHDRAWAL

### 4.1 Inclusion Criteria

1. Diagnosis: Subjects with a diagnosis of head and neck cancer biopsy proven, and who are candidates for radiation therapy
2. Age: Subjects must be  $\geq 18$  years of age and  $\leq 90$  years old.
3. Informed Consent: All subjects must be able to comprehend and sign a written informed consent document.

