### 4.2 Exclusion Criteria

1. Subjects who are pregnant or may become pregnant during metformin administration. Pregnancy testing will be done in conjunction with preradiation protocols.
2. Subjects on metformin for any reason during the preceding 4 weeks.
3. Diabetic subjects are eligible if they are not taking metformin or insulin

4. Subjects who have received iodinated contrast dye must wait 12 hours prior to starting Metformin. If a CT scan with contrast is scheduled after screening and consent, the metformin cannot be taken until after the CT with contrast has been completed and they have waited 12 hours.
5. Patients with plasma creatinine level greater than 1.3 mg/dL.
6. Patients with plasma bicarbonate less than 22 mEq/L or history of lactic or any other metabolic acidosis.
7. Patients with history of congestive heart failure.
8. Patients with myocardial ischemia or peripheral muscle ischemia.
9. Patients with sepsis or severe infection.
10. Patients with history of lung disease currently requiring any supplemental oxygen treatment.
11. Patients scheduled for radiation less than 6 days from enrollment
12. Patients with history of hepatic dysfunction or hepatic disease and abnormal liver function tests. Patients who have a history of hepatic dysfunction or hepatic disease and normal liver function tests will be eligible to participate.
13. Patients with a current history (in the past 30 days) of having drinking which is defined in accordance with CDC definition as more than 8 drinks per week for women and more than 15 drinks per week for men. A standard drink contains .6 ounces of pure alcohol. Generally, this amount of pure alcohol is found in 12-ounces of beer, 8-ounces of malt liquor, 5-ounces of wine, 1.5-ounces or a “shot” of 80-proof distilled spirits or liquor (e.g., gin, rum, vodka, or whiskey). While on study, patients should limit their alcohol consumption to no more than 8 drinks per week for women and no more than 15 drinks per week for men. Patients who feel they cannot comply with this recommendation are not eligible

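### The documents conflict on whether surgery-first patients give their only baseline sample before or after the operation; a pre-surgery baseline would add variance, but not bias, to the primary contrast

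*Combined protocol and SAP*

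**What the plan says.** Section 6.1 of the combined protocol and SAP describes one Visit 1 for everyone. Eligible subjects "will be approached the day of their follow up after initial biopsy"; if they agree, "blood and saliva will be collected, and participant will be randomized", and the questionnaires are given at the same visit. On screening it adds: "Labs for the screening part will be available from pre-admission testing that is standard of care". The schema in section 3.1 covers patients planned for "definitive treatment by definitive radiation or up front surgery followed by adjuvant radiation". Appendix A shows one pre-treatment sample, at Visit 1. The next is in the third week of radiation, and Visit 3 follows two weeks after radiation ends.

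Other wording points to later entry. The Study Summary describes subjects "who have a scheduled appointment for either postoperative adjuvant radiation or definitive radiation". Section 6.1 itself has the drug start date set at Visit 1 from the planned radiation date, with a first dose "at any point from 1 to 7 days from the start of radiation". Section 3.1 moves from consent to study drug without placing an operation between them.

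The eligibility criteria do not settle it. Section 4.1 asks for subjects "who are candidates for radiation therapy". Section 4.2 excludes "Patients scheduled for radiation less than 6 days from enrollment", which sets a minimum gap between enrolment and radiation but no maximum.

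The primary contrast in section 7.1 is the between-arm difference in mean change from baseline to post-treatment. The fixed effects are arm, time and arm by time. Section 5.4 specifies permuted blocks and names no stratification factor.

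**The concern.** Study drug is tied to the start of radiation, not to surgery. A surgery-first patient enrolled at the post-biopsy visit would therefore have the operation and recovery between baseline and first dose, and no later pre-drug sample could separate them out. A definitive-radiation patient would have no such interval. Pooling the two kinds of change in a model with no term for setting puts the difference between them into the residual.

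Staff who follow 6.1 would take a pre-surgery baseline; staff who follow the Summary would take a post-surgery one. The trial could end up with both. At 25 per arm, with planned detectable differences of 0.8 to 1.1 SD, there is little precision to spare.

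**Working it through.** **1. Reproduce the plan (section 7.4).** Inputs: 25 per arm, 40 cytokines, FDR 5%, 80% power per test; exosomes at two-sided alpha 0.05.

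- Single-test alpha for K = 5 by the Jung formula: 0.8 × 5 × 0.05 / (35 × 0.95) = 0.0060, as tabled.
- Detectable difference for K = 5 (two-sided two-sample t-test, noncentral t): 1.06 SD, which rounds to the tabled 1.1.
- Exosomes: detectable difference 0.809 SD; power at 0.81 SD is 80.1%, as stated.

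**2. Variance added by a pre-surgery baseline.** Let f be the share of patients with surgery after baseline, and d the mean surgical shift still present at Visit 3, in units of the SD of change without surgery. The documents give neither. Assumed ranges: f = 0.3 to 0.7, d = 0.5 to 1.5.

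SD multiplier = √(1 + f(1 − f)d²)

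- Smallest: f = 0.3 or 0.7, d = 0.5: √(1 + 0.21 × 0.25) = 1.026
- Middle: f = 0.5, d = 1: √(1 + 0.25 × 1) = 1.118
- Largest: f = 0.5, d = 1.5: √(1 + 0.25 × 2.25) = 1.250

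**3. Power at the same absolute difference, if the planning SD excludes surgery.** Each planned difference is divided by the multiplier.

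| Case | SD of change | Exosome power at 0.81 SD | Exosome detectable difference | K = 5 cytokine power at 1.06 SD |
|---|---|---|---|---|
| No surgery effect | 1.00 | 80% | 0.81 | 80% |
| Smallest | +3% | 78% | 0.83 | 77% |
| Middle | +12% | 71% | 0.90 | 68% |
| Largest | +25% | 61% | 1.01 | 55% |

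The cytokine column starts from the unrounded 1.06 SD so that it begins at the plan's 80%. At the rounded 1.1 SD the start is 84%, and the middle case gives 72%.

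If the surgical effect also varies between patients with SD t, the variance gains f·t². At f = 0.5, d = 1, t = 0.5 it is 1 + 0.25 + 0.125 = 1.375. The SD rises 17%, exosome power is 67% and cytokine power 62%.

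**4. Bias and type I error.** A simulation of 40,000 runs gave both arms the same surgical shift, with f = 0.5. At d = 1, bias was −0.0008, type I error 5.0% and power at 0.81 SD 70.5%. At d = 1.5, bias was 0.00003, type I error 5.1% and power 60.9%. The formula gives 70.9% and 61.2%.

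**The case against.** The strongest reply is that post-operative entry is what was meant. The Summary wording, the setting of the drug start date at Visit 1 and the move from consent to drug in 3.1 all fit it. So does the bottle being handed out at enrolment (section 5.6). Section 5.3 still refers to dosing up to the day before surgery, which does not fit this trial, so the pre-admission laboratory wording could be carried over too; that is inference. This stands to the extent that surgery inside the change score is one reading of a conflict and not a fact. It does not remove the conflict, because 6.1 is the visit instruction and gives post-operative patients no separate path.

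A reader might go further and infer that the change cannot be attributed to metformin. The documents do not support that. The estimate is a randomized contrast with placebo, surgery is expected equally in both arms, and the simulation shows no bias.

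A reader might also infer that the stated 80% power is wrong. It is not. Section 7.4 works only in SD units and gives no source for the SD. If that SD describes the enrolled mix, any surgical heterogeneity is already in it.

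The assumed shift is also open to challenge. It must persist to Visit 3, and section 1.6 plans 8-10 weeks of drug exposure alone, so a short-lived surgical response may have faded. Nor need one shift apply to all analytes.

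**Conclusion.** The documents disagree on when surgery-first patients enter, and the disagreement decides what the primary baseline means for them. A literal reading of 6.1, or mixed practice, would put surgery inside the change score for some patients. The consequence is lost precision, with no bias and no inflation of type I error.

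The size cannot be found from the documents. The losses in the table rest on three assumptions: the surgical share, a shift that lasts to Visit 3, and a planning SD that excludes surgery. If the third fails, the stated power stands and only the absolute detectable difference grows. In a pilot this is a clarification worth making before enrolment, not a flaw that invalidates the analysis.

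**What to change.** - Reconcile the Study Summary, section 3.1, section 6.1 and Appendix A. State that for post-operative patients the baseline blood and saliva, the questionnaires and randomization take place after surgery, once radiation is scheduled and before the first dose.
- Add radiation setting (definitive or post-operative) and setting by time as fixed effects in the 7.1 model.

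The two parts work together. The model term removes the average difference between settings under either baseline, but it cannot remove the spread that arises if some post-operative patients are sampled before surgery and others after. In the calculation above, removing the mean shift returns power to about 80% when the surgical effect is uniform.

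The cost is a wording amendment and a few degrees of freedom. No samples or patients are added, and setting is known at entry. A post-operative baseline may still reflect healing; the setting-by-time term absorbs that on average, but not its variation between patients.

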## **1.5 Study Therapy**

### **Description of the experimental product:**

Metformin is a biguanide oral antidiabetic drug. It inhibits hepatic glucose production, decreases intestinal absorption of glucose, and improves insulin sensitivity thereby increasing peripheral glucose uptake and utilization without causing hypoglycemia. It is an FDA approved medication for the management of type 2 diabetes mellitus with extensive safety data. In general, clinically significant responses are not seen at doses <1500 mg daily; however, a lower recommended starting dose and gradual increased dosage is recommended to minimize gastrointestinal symptoms. Metformin's main effect on cells is to decrease mitochondrial oxidative phosphorylation (OXPHOS) complex I activity. Metformin treatment does not induce hypoglycemia. Metformin may represent a novel radioprotectant therapy.

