**Description and justification for the route of administration, dosing regimen and treatment period:**

Metformin will be administered orally since this is the route of administration currently approved by the FDA. Beginning one-two weeks prior to planned external beam radiation therapy, the drug will be initiated at a dose of 500mg orally daily for 3 days and will then be increased to 500 mg twice daily. If tolerated, metformin will be further increased to 1000mg twice daily after day 6. Subjects will maintain 1000 mg twice a day dosing until two weeks post radiation.

There are currently multiple studies on-going using doses from between 500 mg twice daily up to 2500 mg per day in the treatment arms. There are also studies using the extended release form for a dose of 1500 mg daily. We have chosen our starting dose and escalation regimen to minimize side effects. The chosen standing dose is based on metformin's therapeutic range (minimal therapeutic dose in diabetic patients is 1500-2000 mg a day). The time of planned exposure to metformin will be 8-10 weeks. We will allow a window of an additional 2 weeks in the event that there are delays in the treatment scheduling but no patients will receive metformin for more than 12 weeks.

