#### **5.2 Treatment Regimen**

Metformin is the therapeutic agent in the protocol. The initial starting dose will be 500mg orally daily for 3 (+2 days) days which then will be increased to 500 mg twice daily and, if tolerated, further increased to 1000mg twice daily after day 6 (+ 2 days). Patients will maintain 1000 mg twice a day dosing until 2 weeks after completing their radiation. This dose schedule has been shown to be well tolerated.

The placebo will be dosed as 1 tab BID and will not have a dose escalation.

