#### **5.8 Packaging**

The study drug will be provided by the Department of Otorhinolaryngology and will be coordinated through the Thomas Jefferson University Hospital Investigational Drug Service (IDS) Pharmacy. The study drug will be packaged in 1 bottle containing 500mg tablets for a maximum of 8 weeks.

The bottle will be labeled “take one tablet daily for three days then one tablet twice daily for three days then two tablets twice daily until two weeks after radiation therapy ends”.

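### Sections 1.6 and 6.1 give study-drug start windows that meet only at day 7, and 6.1 lets metformin patients begin radiation before the dose ramp is complete

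*Combined protocol and SAP*

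**What the plan says.** Three sections of the combined protocol and SAP speak to when study drug starts.

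- Section 1.6: "Beginning one-two weeks prior to planned external beam radiation therapy, the drug will be initiated at a dose of 500mg orally daily".
- Section 6.1, Visit 1: "The exact date to start the metformin will be determined this visit based on the planned start of radiation", followed by "Subject will be instructed to start taking the metformin/placebo at any point from 1 to 7 days from the start of radiation". The sentence does not say whether the days fall before or after radiation begins.
- Section 3.1: "After informed consent is signed, patients will be administered metformin with dose escalation as tolerated", and the same sentence runs this phase up to the time of radiation. It gives no number of days.

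The ramp to 1000 mg twice daily is worded in several ways.

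- Section 3.1: "followed by 500 mg twice daily for 3 days followed by 1000mg twice daily from day 6 (+2 days".
- Section 5.2: "if tolerated, further increased to 1000mg twice daily after day 6 (+ 2 days".
- Bottle label (5.8, 5.12.3): "one tablet daily for three days then one tablet twice daily for three days then two tablets twice daily".
- Section 5.3 attaches a 2-day allowance to each of the two 3-day steps.

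Placebo has no ramp (5.2). Exclusion 11 (4.2) bars patients whose radiation is less than 6 days from enrollment. On supply, 1.6 plans 8 to 10 weeks of exposure with a ceiling of 12 weeks. Sections 5.5, 5.8 and 5.12.3 provide a supply of at most 8 weeks in one bottle.

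**The concern.** Metformin is being tested as a radioprotectant, so the dose being taken when radiation begins is part of the intervention. The site cannot satisfy both 1.6 and 6.1 unless the patient starts exactly 7 days ahead. The instruction given to the patient is the one in 6.1, and it allows leads shorter than the ramp. Because only metformin has a ramp, any resulting spread in early dose arises within the metformin arm alone. Unless the dates are recorded, it could not be described afterwards. The 8-week bottle raises a related exposure question: a patient on the planned 10-week course could run out of drug before Visit 3, the first sample after radiation.

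**Working it through.** **Windows.** Section 1.6 gives {7, ..., 14} days before radiation. Section 6.1, read as before, gives {1, ..., 7}. The intersection is {7}. Read as after, the intersection is empty.

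**Plan's own ramp figure.** 3 days at 500 mg/day plus 3 days at 1000 mg/day = 6 days, so full dose (2000 mg/day) begins on drug day 7. The label gives the same. With both allowances in 5.3, the ramp is 3 + 2 + 3 + 2 = 10 days and full dose begins on drug day 11.

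**Days below full dose after radiation begins.** Let s be the lead in days and F the first full-dose drug day. The first fraction falls on drug day s + 1, so days below full dose = max(0, F − 1 − s). These are calendar days, because the documents give no fraction schedule.

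| Lead s | F = 6 (3.1) | F = 7 (label) | F = 9 (5.2, +2 used) | F = 11 (5.3, both +2 used) |
|---|---|---|---|---|
| 1 | 4 | 5 | 7 | 9 |
| 2 | 3 | 4 | 6 | 8 |
| 3 | 2 | 3 | 5 | 7 |
| 4 | 1 | 2 | 4 | 6 |
| 5 | 0 | 1 | 3 | 5 |
| 6 | 0 | 0 | 2 | 4 |
| 7 | 0 | 0 | 1 | 3 |
| 8 | 0 | 0 | 0 | 2 |
| 9 | 0 | 0 | 0 | 1 |
| 10 | 0 | 0 | 0 | 0 |

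Start days with an unfinished ramp:

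- Section 6.1 window: 4, 5, 7 and 7 of 7.
- Section 1.6 window: 0, 0, 1 and 3 of 8.

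**Milligrams short at a 1-day lead.** Each day at 500 mg is 1500 mg short, and each day at 1000 mg is 1000 mg short.

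- F = 6: 2 × 1500 + 2 × 1000 = 5,000 mg.
- F = 7: 2 × 1500 + 3 × 1000 = 6,000 mg.
- F = 9 (5 days at 500 mg, 3 at 1000 mg): 4 × 1500 + 3 × 1000 = 9,000 mg.
- F = 11 (5 days at each): 4 × 1500 + 5 × 1000 = 11,000 mg.

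**As a share of full dose.**

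- First fraction to the week-3 sample is 14 to 20 days, or 28,000 to 40,000 mg. The 6,000 mg is 15.0 to 21.4%; the 11,000 mg is 27.5 to 39.3%.
- To Visit 3, assuming 5 to 7 weeks of radiation, is 49 to 63 days, or 98,000 to 126,000 mg. The 6,000 mg is 4.8 to 6.1%; the 11,000 mg is 8.7 to 11.2%.
- For reference, the planned 8 to 10 weeks less the 1.6 lead and the 2-week tail implies 8 − 1 − 2 = 5 to 10 − 2 − 2 = 6 weeks of radiation.

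**Supply.** The bottle covers 56 days. Ten weeks is 70 days (14 short); the 12-week ceiling is 84 days (28 short). Neither comparison needs a radiation length. Metformin tablets by label = 3 + 6 + 4(n − 6); placebo capsules = 2n.

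| Days n | Metformin | Placebo |
|---|---|---|
| 56 | 209 | 112 |
| 70 | 265 (+56) | 140 (+28) |
| 84 | 321 (+112) | 168 (+56) |

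**The case against.** The best defence is that the intended sequence can be inferred. Section 3.1 puts escalation ahead of radiation, exclusion 11 reserves the nominal ramp length, and one exact date is set for each patient at Visit 1. On that view the fault is one loosely worded sentence in 6.1. This stands in part, but exclusion 11 governs enrollment and not the first dose. A patient enrolled in good time may still be told to start 1 day ahead. Exclusion 11 also admits a patient exactly 6 days out, who cannot meet 1.6.

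Several stronger readings are tempting, and the documents do not support them.

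- **Ramp doses are inactive.** A reader might infer this from section 1.5: "In general, clinically significant responses are not seen at doses <1500 mg daily". That sentence follows the type 2 diabetes indication, and 1.6 ties its 1500 to 2000 mg range to diabetic patients. No dose threshold for radioprotection or cytokine effects is given.
- **Full dose is required by the first fraction.** No section says so.
- **Most patients will start too late.** Five of seven counts permitted days, not patients. The actual spread of starts is unknown.
- **6.1 means after radiation begins.** The wording allows it, but a date set from the planned start of radiation, together with 3.1, points to before.
- **The primary comparison is compromised.** The contrast in 7.1 is baseline to post-treatment, and no week-3 contrast is specified. By label, even a 1-day lead leaves at least 14 − 5 = 9 full-dose days before the week-3 sample.

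**Conclusion.** The inconsistency is real and worth correcting; its consequence is modest. The two windows share one day. As written, 6.1 permits radiation to begin mid-ramp on 4 or 5 of its 7 start days under the nominal wordings, and on all 7 with the 5.2 allowance used in full. The upper bound is 9 calendar days below full dose and 11,000 mg short. The result is variable early exposure within the metformin arm. It does not invalidate the randomized comparison and changes no power, alpha or sample-size figure. The counts assume that 6.1 means before radiation, and the Visit 3 percentages also assume 5 to 7 weeks of radiation. The supply gap, 8 weeks dispensed against 8 to 10 planned, is a separate conflict that rests on the protocol's own figures.

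**What to change.** In 1.6, 3.1 and 6.1, state one window: start 6 to 14 days before the first radiation fraction, earlier in the window where timing allows. Six days completes the label ramp and fits exclusion 11, so no patient becomes ineligible. Ten days are needed to absorb both allowances in 5.3; an 8-day lead would not be enough.

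If a contrast CT after consent shortens the lead, start once the required hold ends, keep the patient in the trial and do not delay radiation. Record the dates of first dose, first full dose and first fraction, and report them by arm. Part of this may already exist, since calls are made on escalation days (1.6, 5.3) and phone logs are source documents (9.2).

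Separately, dispense for the planned duration, or resupply at Visit 2, where medication is already inventoried. Do this identically in both arms so that resupply does not reveal assignment to patients. Against a 56-day supply, 70 days needs 56 more metformin tablets or 28 more placebo capsules per patient; 84 days needs 112 or 56.

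The cost is wording in three sections, three dates and a small extra supply. Some short leads will remain after contrast CT.
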